13. SPECIMEN BANKING

- *If specimens will be banked for future research, describe where the specimens will be stored, how long they will be stored, how they will be accessed and who will have access to the specimens*
- *List the information that will be stored with each specimen, including how specimens are labeled/coded*
- *Describe the procedures to release the specimens, including: the process to request release, approvals required for release, who can obtain the specimens, and the information to be provided with the specimens.*

NA

14. DATA MANAGEMENT AND CONFIDENTIALITY

- *Describe the data and specimens to be sent out or received. As applicable, describe:*
 - *What information will be included in that data or associated with the specimens?*
 - *Where and how data and specimens will be stored?*
 - *How long the data will be stored?*
 - *Who will have access to the data?*
 - *Who is responsible for receipt or transmission of data and specimens?*
- *Describe the steps that will be taken to secure the data during storage, use and transmission.*

[The research material collected will include quantitative and medical record abstraction data at the time of screening. The quantitative and electronic medical record data will be collected specifically for the proposed research project. The medical chart data is collected to contact the patient at follow-up time points. Signed hard-copy informed consents will be kept in a locked file cabinet at [name]. Only the study personnel will have access to links between subjects and subject identities. Access to the Northwell Health SharePoint PHI drive containing electronic data is restricted to study personnel.

Data will be collected through REDCap (Research Electronic Data Capture), a vetted HIPAA-compliant (Health Insurance Portability and Accountability Act) web-based application that manages research surveys and databases. All data will be de-identified prior to conducting analyses. Only the PI and IRB approved study team will have access to the links that can associate the subject record to the individuals. These links will be maintained in REDCap. Subjects will sign an informed consent form prior to partaking in the study that states the potential risk of loss of confidentiality. This risk will be mitigated by storing data appropriately, ensuring only study personnel have access to the data, and that there are data use agreements in place before data is shared.

Research data and documentation will be maintained securely and stored in REDCap and on Northwell's SharePoint PHI drive according to applicable regulatory requirements (Policy 100.97 Records Retention and Destruction and GR021 Research Data Ownership and Management for additional information).

The Principal Investigator will meet with the study staff on a regular basis to ensure data accuracy and protocol adherence. To ensure the validity and integrity of study data, the PI will also oversee all data management responsibilities across both sites.]

15. DATA AND SAFETY MONITORING PLAN

A specific data and safety monitoring plan is only required for greater than minimal risk research. For guidance on creating this plan, please see the [Guidance Document](#) on the HRPP website.

*Part I – this part should be completed for all studies that require a DSMP.
Part II – This part should be completed when your study needs a Data and Safety Monitoring Board or Committee (DSMB/C) as part of your Data and Safety Monitoring Plan.*

Part I: Elements of the Data and Safety Monitoring Plan

- *Indicate who will perform the data and safety monitoring for this study.*
- *Justify your choice of monitor, in terms of assessed risk to the research subject's health and well being. In studies where the monitor is independent of the study staff, indicate the individual's credentials, relationship to the PI, and rationale for selection*
- *List the specific items that will be monitored for safety (e.g. adverse events, protocol compliance, etc)*
- *Indicate the frequency at which accumulated safety and data information (items listed in # above) will be reviewed by the monitor (s) or the DSMB/C.*
- *Where applicable, describe rules which will guide interruption or alteration of the study design.*
- *Where applicable, indicate dose selection procedures that will be used to minimize toxicity.*
- *Should a temporary or permanent suspension of your study occur, in addition to the IRB, indicate to whom will you report the occurrence.*

Oversight Responsibilities:

The Principal Investigator (PI), [name], has oversight responsibility for the conduct of this research. The PI will supervise the research, ensure that each individual engaged in research is qualified to do so by virtue of education, training and experience to perform the delegated task. He will protect the rights, safety and welfare of participants by ensuring that the research is conducted in accordance with all federal regulatory requirements, state law and Northwell Health policies (including IRB SOPs) and with the IRB-approved plan, and is conducted in accordance with the IRB approved plan, and ensure the accuracy, security and integrity of the research data and data analysis.

Monitoring Responsibilities:

Study data are accessible at all times for review by the PIs and named co-investigators. The PI and co-investigators will review study on a monthly basis. Coordinators will be able to monitor study procedure adherence through remote monitoring. Any technical issues with the Bottle Cap messaging will be addressed directly by the study team and a dedicated Bottle Cap technical and customer support group.

- Reportable events (unanticipated problems, deviations, violations, etc.) will be reviewed by the PIs at each site and reported to their respective IRBs in a timely manner and in accordance with local IRB Policy.

All events determined to be reportable at the collaborating VA site will be communicated to the Northwell Health PI to assess changes as/if needed to the research.

In addition to reportable events, deviations will also be monitored. Deviations can be the results of actions of the participant or of the study team. For example, situations in which the investigator failed to perform tests or examinations as required by the protocol or failures on the part of study subjects to complete scheduled visits as required by the

protocol, would be considered protocol deviations. Protocol deviations can be major or minor.

Major Protocol Deviation: A deviation that affects subject safety, rights, welfare or data integrity.

Examples of major protocol deviations include (but are not limited to):

- Use of study procedures not approved by the IRB
- Failure to report unanticipated problems to the IRB and/or sponsor
- Enrollment of subjects (or use of their identifiable data) after IRB-approval of study expired

Minor protocol deviation: A deviation that does not affect subject safety, rights, welfare or data integrity.

Examples of minor protocol deviations include (but are not limited to):

- Deviations from the approved study procedure that do not affect subject safety or data integrity
- Omitting an approved portion of the protocol

The PIs will determine if a deviation is major or minor. Major protocol deviations will be reported to the IRB within ten (10) working days of discovery. Minor protocol deviations will be reported at the time of continuing review or check-in by the IRB.

For this study, research procedures are limited to receipt of text messages and completion of questionnaires/surveys. As such, we do not expect adverse events (AE) to occur. However, if they do, adverse events will be reported to the IRB per reporting guidelines, unless they are attributable to a medically indicated procedure accompanying participation in this protocol. Non-serious adverse events will not be reported in the IRB at each occurrence but will be reported in summary form at the time of continuing review and protocol termination. Serious adverse events will be reported using the serious adverse event report form.

Despite all of our efforts to maintain the privacy and data security of our participant's information, unanticipated problems, such as a stolen computer may occur, although it is highly unlikely. OHRP considers unanticipated problems, in general, to include any incident, experience, or outcome that meets all of the following criteria:

1. unexpected (in terms of nature, severity, or frequency) given (a) the research procedures that are described in the protocol-related documents, such as the IRB-approved research protocol and informed consent document; and (b) the characteristics of the subject population being studied;
2. related or possibly related to participation in the research; and
3. suggests that the research places subjects or others at a greater risk of harm (including physical, psychological, economic, or social harm) than was previously known or recognized.

Unanticipated problems can be "acts of God", power failures, breaches of confidentiality, loss of study data, etc. since they could have an adverse effect on study subjects.

Related: An event is “related” if it is likely to have been caused by the research procedures.

Probably/Possibly Related: An event is considered to be probably or possibly related to the research if there is a greater than 50% chance that the event was caused by the study procedures.

Should an unanticipated event related to the research that exposes individuals other than the research participants (e.g., investigators, research assistants, students, the public, etc.) to potential risk, the event will be reported in a timely manner but not more than five (5) working days after discovery by the PI.

The PIs, as well as the IRB and other oversight committees, have the authority to stop or suspend the study or require modifications.

Part II: Data and Safety Monitoring Board or Committee

- *When appropriate, attach a description of the DSMB.*
- *Provide the number of members and area of professional expertise.*
- *Provide confirmation that the members of the board are all independent of the study.*

| |
|--|
| |
|--|

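### The more-than-50% bar for 'possibly related' is in effect no lower than 'related', so less certain events are not classed as unanticipated problems

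*Combined protocol and SAP*

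**What the plan says.** All the relevant text is in Section 15, Part I.

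- **Unanticipated problem.** It is "any incident, experience, or outcome that meets all of the following criteria". Three criteria follow: the event is unexpected, it is "related or possibly related to participation in the research", and it suggests a greater risk of harm than was known.
- **Related.** An event is related "if it is likely to have been caused by the research procedures". No percentage is attached.
- **Probably or possibly related.** This is a single tier, which applies "if there is a greater than 50% chance that the event was caused by the study procedures".
- **What follows from the label.** "Reportable events (unanticipated problems, deviations, violations, etc.) will be reviewed by the PIs at each site", and they then go to that site's IRB in a timely manner under local policy. Between sites, "All events determined to be reportable at the collaborating VA site will be communicated to the Northwell Health PI".
- **Adverse events.** These have their own route: "adverse events will be reported to the IRB per reporting guidelines". Serious events go on a dedicated form, and non-serious events are summarised at continuing review and at termination. The one stated exception is an event attributable to a medically indicated procedure that accompanies participation.

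**The concern.** A criterion worded as related *or possibly related* is meant to catch two kinds of event: those that the study probably caused, and those where a study cause is plausible but less certain. The definitions remove the second kind. *Possibly* is tied to *probably* at a better-than-even chance, so no category is left between likely and unrelated.

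What is at stake is how uncertain events are classified and how quickly they are handled. An event screened out on relatedness need never be tested against the third criterion, which asks whether the research carries more risk than was thought. A narrow definition also narrows the set of VA events that must be sent to the lead investigator.

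**Working it through.** The 50% is a definitional cut-off, not a calculated figure, so there is nothing to recompute. The check sets the definitions side by side and traces which reporting routes depend on them.

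**1. The relatedness criterion.** Let *p* be the assessor's chance that the study caused the event, and let *L* be the unstated level at which causation counts as likely. The criterion is met if *p* exceeds *L* (related) or *p* exceeds 50% (probably or possibly related).

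- If *L* is 50%, the ordinary meaning of likely, both tiers have the same bar and *possibly* adds nothing.
- If *L* is above 50%, *possibly* adds only the band from 50% to *L*. Events at 50% or less still fail.
- Only if likely meant less than an even chance would some events at or below 50% qualify. They would do so as related, and *possibly related* would then be the stricter label, which reverses the usual order.

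On any ordinary reading, an event with *p* above 0 and up to 50% fails. All three criteria must be met, so it is not an unanticipated problem.

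**2. What happens to an event with *p* of 50% or less.**

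| Route in Section 15 | Depends on the 50% definition? | Result |
|---|---|---|
| Classed and reported as an unanticipated problem | Yes | Not classed |
| Sent from the VA site to the lead investigator as reportable | Yes, where the ground is an unanticipated problem | Not required on that ground |
| Serious adverse event form | No threshold stated | Still reported |
| Non-serious adverse event summary | No threshold stated | Still reported, but only at continuing review and termination |
| Deviations and violations | No | Still reported if the event is also one of these |

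An incident that is not an adverse event, such as lost data, has no other stated route in this range unless it is also a deviation or violation or local IRB policy catches it.

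**3. The plan's own examples.** Section 15 says that unanticipated problems can include acts of God, loss of power, confidentiality breaches and lost data, and it mentions a stolen computer. An act of God or a power failure could hardly be more than 50% likely to have been caused by study procedures. Read literally, the definition shuts out events that the same section lists as included.

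**4. Where the gap falls.** Sections 17 and 18 name distress from questions about cancer or drinking as the foreseeable risk. Section 3 describes survivors who live with severe long-term changes in function and quality of life. With competing causes of that kind, an assessor may well find a study contribution plausible without putting it above 50%. An unexpectedly severe or frequent reaction could then stop at the relatedness criterion.

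**The case against.** The strongest reply is that little goes unreported. Adverse events reach the IRB whatever their relatedness. A reader might infer from the 50% bar that less certain events fall outside reporting, or that the safety count will be too low. The documents do not support either inference: adverse event counts do not use this definition, and only the count of unanticipated problems could be lower.

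A reader might also infer that reporting is the only safeguard, since no independent monitor is described. That is not supported either. Section 15 provides monthly review by the investigators and authority to stop, suspend or modify the study. Section 27 adds monthly review of safety concerns and lets anyone raise one between meetings. Section 18 provides social work referral for participants who express distress. The Section 15 template asks for a specific monitoring plan only when risk is more than minimal, and Section 18 states that it is not.

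Three further points have some force.

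- *Related* has no percentage, so the equality of the two bars is an inference from the word likely. It is the natural reading, and step 1 shows that the gap at 50% or less does not depend on exact equality.
- The listed examples suggest that the 50% test was not meant as a strict causal filter. That may be the intention, but it is a reason to correct the wording, because the stated rule says otherwise.
- Reporting follows local IRB policy, which may define relatedness more broadly. That could soften the effect in practice, but the policy is not in the documents and does not repair the protocol's own definition.

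**Conclusion.** The point holds in a narrow form. As written, *possibly related* does no work below the level of likely. An event with a real chance of causation of 50% or less is therefore not classed or promptly handled as an unanticipated problem, and it is not necessarily passed from the VA site to the lead investigator as reportable. Reporting of adverse and serious adverse events stands as it is.

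This rests on reading likely as at least an even chance and on applying the definitions literally. The number of events affected cannot be estimated from the documents and is probably small, because the procedures are text messages and questionnaires in a study described as minimal risk. This is a minor but real defect in a stated rule, and it has no bearing on the endpoints, analyses or sample size.

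**What to change.** Split the merged tier in Section 15:

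- leave *related* as it is;
- keep the more-than-50% wording for *probably related* only;
- define *possibly related* with a lower bar than *related*, for example a reasonable possibility that the research contributed to the event, even if another cause is more likely.

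Referring to the research as a whole in the last definition, and not only to its procedures, would also bring it into line with the wording of the criterion and with the plan's own examples. The same definitions should be used at both sites, so that the VA team and the lead team judge what is reportable in the same way.

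The cost is a change to one definition and possibly a few more reports to the IRB.

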16. WITHDRAWAL OF SUBJECTS

- *Describe anticipated circumstances under which subjects will be withdrawn from the research without their consent*
- *Describe procedures for orderly termination*
- *Describe procedures that will be followed when subjects withdraw from the research, including partial withdrawal from procedures with continued data collection.*

Circumstances in which participants may be withdrawn from the research without their consent may include the following:

- failure to follow instructions,
- failure to adhere to scheduled in-person or virtual interviews,
- it is not in the participant’s best interest to continue on this study, or
- the study is stopped.

This decision may be made by the PIs, or the IRB.

Participants will be able to withdraw from the study at any time. The consent form will make explicit to patients that they may discontinue the study at any time without penalty and without prejudice to their medical care.

Any subjects withdrawn from the research will be instructed that per the consent form we may still use information we have already collected for research purposes but will not

continue to collect any further data. The subject will have their information removed from any future correspondence that was planned for the study.]

17. RISKS TO SUBJECTS

- *Describe any potential risks and discomforts to the subject (physical, psychological, social, legal, or other) and assess their likelihood and seriousness and whether side effects are reversible. Where appropriate, describe alternative treatments and procedures that might be advantageous to the subjects.*
- *Include risks to others, like sexual partners (if appropriate)*
- *Discuss why the risks to subjects are reasonable in relation to the anticipated benefits and in relation to the importance of the knowledge that may reasonably be expected to results*
- *Describe the procedures for protecting against or minimizing any potential risks, including risks to confidentiality, and assess their likely effectiveness.*

[There is a slight risk that participants might be distressed or uncomfortable when being asked questions about their cancer or drinking habits. All research personnel with patient contact will be trained by [name] and the Co-Is to be vigilant and sensitive to expressions of distress. All participants will be encouraged to contact the PI if any concerns arise.

The risks to subjects are reasonable in that this is a minimally invasive study, no subject's treatment will be altered in any way and the only potential risk is that of distress with questions being asked which they are free to skip. The risks are outweighed by the anticipated benefits and knowledge to be gained that may help HNC survivors in addition to providing subjects with enhanced knowledge and awareness of the risks of alcohol consumption after cancer treatment.

The procedures to protect subjects against or minimize the described risks in addition to risks to confidentiality include allowing participants to skip or choose not to respond to any questions that may cause them distress. Confidentiality will be protected by ensuring that all patient information gathered will be kept on Northwell's secured server and in password protected files that only the research team has access to. Further, information will only be accessed when needed and the research team will be trained to ensure confidentiality and the correct procedures when accessing and saving patient information are used.

In the future, we may publish results of this study on data sharing websites (e.g., Open Science Framework), in scientific journals, and may present it at scientific meetings. If we do we will not identify the subject. All data included in the publication will be de-identified.

]

18. RESEARCH RELATED HARM/INJURY

- *Describe the availability of medical or psychological resources that subjects might need as a result of anticipated problems that may be known to be associated with the research.*
- *If the research is greater than minimal risk, explain any medical treatments that are available if research-related injury occurs, who will provide it, what will be provided, and who will pay for it.*

[This study presents no greater than minimal risk to participants, thus research related harm/injury is not expected.]

Patients may be at risk for slight emotional distress, which might result from being asked questions about personal cancer and treatment experiences. Participants will be informed during the interview sessions and at the beginning of the assessment that potentially sensitive topics will be discussed and that they may skip any part that would make them uncomfortable. In accordance with Monter's standard of care procedures, any participant who expresses distress throughout the duration of this study, for any reason, will be referred by the study team to a licensed social worker from our institution. Patients will also be referred to social work if they are clinically depressed or found to have severe substance abuse, as evaluated by our baseline assessment of standardized measures]

19. POTENTIAL BENEFIT TO SUBJECTS

- *Explain what benefits might be derived from participation in the study, noting in particular the benefit over standard treatment (e.g. a once-a-day administration instead of four times a day, an oral formulation over an IV administration).*
- *Also state if there are no known benefits to subjects, but detail the value of knowledge to be gained*

[This research is designed to test the acceptability of this type of intervention program. We also want to test how well it works so we can try this approach with more people in a larger research study. Because we are looking at how well this works, participants may indirectly benefit from learning more about alcohol and its effect on cancer survivors. Information we gather from participants' responses may help future cancer and HNC patients to cut down (reduce) their alcohol drinking.]

